5.2 Primary objectives

To evaluate the volumetric changes on the occlusal surface of the splints after the adjustment done and compare these changes before and after in each group.

5.3 Secondary objectives N/A

6 Study/Trial design & Flowchart.

6.1 Study/Trial Design

This clinical trial will be conducted on 40 participants, each will receive an occlusal devices according to the grouping below. Group

Group	Group A	Group B	Group C	Group D
Criteria	Without digital facebow at ICP	With digital facebow at ICP	Without digital facebow at RAP	With digital facebow at RAP

The clinical and the lab steps:

This clinical trial will need 2 clinical visits:

VISIT ONE:

1-Participant information and informed consent.

Before participation, all participants will be provided with a detailed informed consent form outlining the purpose of the study, the procedures involved, potential benefits, and risks. Participants will be given the opportunity to ask questions before providing written consent.

2-Dental photography including Frontal, Right buccal, Left buccal, Upper occlusal, Lower occlusal views.

3- Digital facebow using the **AxioSnapMount Facebow-Germany**. It typically consists of adjustable earpieces and a bite fork, which are attached to the patient head, the bite fork is inserted into the patient's mouth, and the patient is guided to bite down into occlusion, Once the bite position is scanned, the AxioSnapMount facebow is removed from the patient's head. And the data are transferred as STL file into the program.

4- Digital impression of upper and lower teeth using **Intraoral Scanner (IOS) (Primescan, Sirona)**. Clinical conditions at the time of scanning the patient will be IOS calibrated before each scan according to the manufacture's recommendations, operatory temperature is at room temperature, Optragate will be used to separate the cheeks and saliva suction at the beginning of each arch scan and operatory light will be turned off. The IOS start on the occlusal of the maxillary right second molar, continues along the occlusal surfaces of the adjacent teeth to the left maxillary second molar, continues toward the buccal side of the same left maxillary second molar to the buccal side of the right second molar, and ends with a scan of the lingual side of the same molar to the left maxillary second molar, continues toward the buccal side of the same left maxillary second molar to the buccal side of the right second molar, and ends with a scan of the lingual side of the same molar to the left maxillary second molar.

5- Bite registration: A Lucia gauge will be used to separate the maxillary and mandibular teeth for 5 minutes to deprogram the muscles of mastication. The participant will be guided to occlude on the lucia jig to protrude and perform lateral excursions of the mandible without posterior tooth contacts. The position will be recorded with a polyvinylsiloxane occlusal recording material (O-Bite; DMG). Then the teeth will be dried with an air syringe to minimize the influence of saliva on scanning accuracy. the intraoral scanner will scan the maxillary and mandibular dentition and the maxillomandibular bite relationship in the **retruded articular position (RAP)**. While obtaining the occlusal relationship, the occlusal record will be located on one side to scan the teeth on the other side.

6- Another bite record will be taken where teeth meet normal together, as soon as **Intercuspal position (ICP) and scanned** by the IOS.

LAB PROCEDURE:

1- All groups will be mounted digitally on average value virtual articulator.

Group A. Export the scans for the **CAD design** in Standard Tessellation Language (STL) files and processed for virtual mounting the models on virtual articulator with **average values**. The average digital articulator will use average values (Bennett angle=10 degrees; immediate side shift=0.5 mm; condylar angle=30 degrees; angle incisal table=30 degrees) as its parameters with the use the ICP record.

Group B. The scanned **facebow fork** will be imported and matched to the software for the maxillary mount. And the fabrication of the occlusal splint with the ICP record.

Group C. The models will be mounted using the RAP record only.

Group D. The models will be mounted using the digital facebow and the RAP record.

- 2- **Design** the occlusal splint based on the patient's specific dental anatomy, considering factors like the bite, occlusion, and any specific requirements for the splint.
- 3- **Printing:** load the digital file and a 3D printer Sprintray **will be** used to print all the digital occlusal devices based on the digital design. These digital devices are to be printed from.
- 4- **Polishing:** Apply a biocompatible polish (Sof-Lex™ Finishing and Polishing System by 3M).
- 5- Scan the splint by using lab scanner (3 shape E3) the splint with optical spray to overcome the translucency issue while scanning (Telescan CAD Spray White).

VISIT 2:

Patient fitting

-Try the digital occlusal splint on the patient to ensure a proper fit and make any necessary occlusal adjustment.

-Scan: after the required occlusal adjustments are done, the splints are scanned again.

The next step:

The STL files of both scans of the occlusal device will be imported into a reverse engineering software program (**Geomagic Wrap 2021; 3D Systems**), and the root mean square (RMS) values will be used to represent the volume of occlusal adjustment and will be obtained by the “best fit alignment” and “3D compare” function. the occlusal adjustment positions will be standardized according to the 3D deviation scale diagram in the software program.

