10.1 Randomization Procedures (if applicable)

There is no randomisation in this study as all participants will undergo the same process of scanning and recording.

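### The ICP record is taken after muscle deprogramming for RAP, in the same order for everyone, so any carry-over would be confounded with the RAP-versus-ICP comparison; swapping two steps avoids this.

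*Combined protocol and SAP*

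**What the plan says.** Section 6.1 (Study/Trial Design) sets out Visit One as numbered steps: consent, photographs, digital facebow, digital impression, then two bite records.

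- Step 5: "A Lucia gauge will be used to separate the maxillary and mandibular teeth for 5 minutes to deprogram the muscles of mastication". The RAP record is then made and scanned.
- Step 6: "Another bite record will be taken where teeth meet normal together". This is the ICP record, also scanned.

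No interval between the two is given, and no reason for the order. Section 10.1 (Randomization Procedures) states: "There is no randomisation in this study as all participants will undergo the same process of scanning and recording". The order is therefore neither varied nor counterbalanced.

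The laboratory part of section 6.1 assigns one record to each group:

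- Group A: average-value articulator settings, "as its parameters with the use the ICP record".
- Group B: ICP again, this time with the facebow.
- Group C: "The models will be mounted using the RAP record only".
- Group D: RAP again, this time with the facebow.

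The Endpoints row of the synopsis (section 3) names RAP versus ICP as part of what is compared.

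**The concern.** Step 5 deliberately changes the state of the jaw muscles. Step 6 then records the participant's usual bite in the same sitting. If any of the deprogramming effect persisted, it would enter the ICP record and not the RAP record, for which deprogramming is intended. Position of record (ICP or RAP) and place in the sequence (second or first) would then be the same variable, and a difference between groups A and B on one side and C and D on the other could not be attributed to position alone.

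This cannot be repaired later. Every participant has the same order, so the data contain nothing from which to estimate an order effect. More participants would only estimate the mixed quantity more precisely. Random allocation to groups would not help either, because the order belongs to the record and not to the participant.

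**Working it through.** **Step 1: is the order fixed?** The steps are numbered 5 and 6, step 6 calls its record a further one, and section 10.1 describes one common process. Together these give RAP first and ICP second for everyone. This is an inference, since no sentence states it as a rule, and the step 6 sentence is garbled in the middle.

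**Step 2: which groups are exposed?** From the laboratory procedure in section 6.1, A and B use ICP and C and D use RAP. Exposure to a post-deprogramming ICP record is A yes, B yes, C no, D no.

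**Step 3: which comparisons would be affected?** Let b be the shift in the mean outcome of A and B caused by carry-over, in within-group SD units and of either sign, assumed equal in A and B. With no true differences the group means are A = b, B = b, C = 0, D = 0.

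- ICP minus RAP: (A + B)/2 − (C + D)/2 = (b + b)/2 − 0 = b.
- Facebow effect: [(B − A) + (D − C)]/2 = (0 + 0)/2 = 0.
- Interaction: (B − A) − (D − C) = 0 − 0 = 0.

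The position comparison takes the whole shift; the facebow comparison takes none. If the true ICP-minus-RAP difference is δ, the plan estimates δ + b. The number of participants does not appear in that expression.

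**Step 4: what would a given b do?** The plan's total reproduces: 4 × 10 = 40 (section 13.1). It comes from no power calculation, and the trial's own alpha and SD are not stated. The following therefore assumes two-sided alpha 0.05, no true difference, and values of b chosen for illustration.

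- One-way ANOVA, 4 groups of 10, on 3 and 36 degrees of freedom. Noncentrality = 10 × [4 × (b/2)²] = 10b².
- Direct ICP-versus-RAP test, 20 against 20, normal approximation, SE = √(2/20) = 0.316.

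| Assumed b (SD) | ANOVA rejects | 20 v 20 test rejects |
|---|---|---|
| 0 | 0.050 | 0.050 |
| 0.1 | 0.055 | 0.062 |
| 0.25 | 0.085 | 0.124 |
| 0.5 | 0.212 | 0.353 |
| 1.0 | 0.710 | 0.885 |

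The rates are the same for −b as for +b, so the table says nothing about direction.

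**Step 5: does the reverse order create a mirror-image problem?** With ICP first, no deprogramming precedes it, so b from this source is 0 by construction. The 5 minutes of deprogramming would then lie between the ICP and RAP records, immediately before RAP as now. Closing the teeth before deprogramming is already part of the visit, because the participant bites on the facebow fork in step 3.

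**The case against.** The strongest objection is that no harm is demonstrated. Nothing in the documents says that deprogramming outlasts the RAP record or alters a later closure, and step 6 describes a position where the teeth themselves meet, which should limit any muscle effect. This stands: the point is conditional on carry-over existing.

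A reader might go further and infer that the order can only penalise the ICP groups, and so favours the result the synopsis expects. The documents do not support that.

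- A residual effect could move ICP closure toward RAP, making A and B more like C and D and shrinking the contrast.
- Section 6.1 does not state the jaw position in which the splint is adjusted at Visit 2, so a shifted record could raise or lower the adjustment needed.
- The synopsis sentence is ambiguous. Its explicit subject is the facebow, and less modification with RAP is only one reading.

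A reader might also want to turn an assumed record error into a percentage inflation of the RMS outcome. That would hold only if bite-record error were the sole source of RMS. Mounting, design, printing, polishing, scanning, alignment and the chairside adjustment itself can all contribute.

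Finally, the point is minor beside non-random allocation (section 10.1) and a group size of 10 set by time and finance (section 13.1). That is fair. It argues for a low rating, not for leaving the order as it is.

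**Conclusion.** The point holds as a minor design weakness. As listed, ICP follows deprogramming for every participant, only groups A and B use that record, and any carry-over would be fully confounded with the RAP-versus-ICP comparison. If the shift is equal in A and B, the facebow comparison is unaffected.

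The existence, direction and size of carry-over cannot be derived from the documents. On the assumptions in the working, a shift of 0.1 SD would be nearly harmless (ANOVA false-positive rate 0.055), while 0.5 SD would matter (0.212). Neither value is an estimate for this trial. The case for change rests on a low-cost precaution, taken in advance, against an effect that no later analysis could separate out.

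**What to change.** In Visit One of section 6.1, take and scan the ICP record directly after the digital impression (step 4), before the deprogramming device is placed. Then carry out step 5 for RAP unchanged. State that this order applies to all participants, and complete the unfinished step 6 sentence.

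Two steps change places. The number of visits, records, procedures and participants (40) stays the same. That the change is free is inferred from the unchanged list of steps, so the investigators should confirm that nothing practical requires the present order. If something does, the protocol should give the reason and acknowledge the possible order effect when interpreting RAP versus ICP. The swap removes this order effect only and does not address allocation or sample size.

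### The baseline splint scan precedes first seating, so any fit correction at Visit 2 can be counted as occlusal adjustment

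*Combined protocol and SAP*

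**What the plan says.** The measurement steps are all in section 6.1 of the combined protocol and SAP. Under the lab procedure the splint is printed (step 3), polished (step 4) and then scanned (step 5): "Scan the splint by using lab scanner (3 shape E3) the splint with optical spray to overcome the translucency issue while scanning". This is the only scan before adjustment.

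The splint first meets the patient at Visit 2, where a single step reads: "Try the digital occlusal splint on the patient to ensure a proper fit and make any necessary occlusal adjustment". The next line gives the second scan: "after the required occlusal adjustments are done, the splints are scanned again". Section 10.3 also lists insertion, fitting and occlusal adjustment together, with fitting named as an act of its own.

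For the outcome, "The STL files of both scans of the occlusal device will be imported into a reverse engineering software program". The two scans are aligned by best fit, and "the root mean square (RMS) values will be used to represent the volume of occlusal adjustment". The only sentence on where adjustment is located is "the occlusal adjustment positions will be standardized according to the 3D deviation scale diagram in the software program".

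Section 5.2 names a narrower target: "To evaluate the volumetric changes on the occlusal surface of the splints after the adjustment done". The synopsis likewise refers to the biting surface, and says the outcome will show how accurately each technique captures the bite registration.

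**The concern.** The trial has one objective, and the RMS is the only measure given for it. That RMS is meant to show how well each combination of bite record and facebow predicted the occlusion. It can do so only if what happens between the two scans is occlusal adjustment.

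As written, the interval between the scans also contains the first seating and whatever is done to make the splint fit. Seating depends on the arch scan, the design and the print, which follow the same steps in all four groups. It does not depend on the position in which the bite was recorded or on whether a facebow was used. A splint that needed correction to seat could therefore score as if its bite record were poor.

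At stake is precision. Change unrelated to the bite record adds variation between splints and compresses the differences between groups. Section 13.1 accepts 10 splints per group where it would have preferred 30, so there is little room for avoidable noise.

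**Working it through.** The plan gives no RMS value, scan error or expected difference, so it has no figure to reproduce on this point. The check has two parts: the order of events, and an illustration with assumed values.

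**Order of events (section 6.1)**

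| Step | Where | Change to the splint | Scan |
|---|---|---|---|
| Print, polish | Lab steps 3–4 | Fabrication | – |
| Baseline scan | Lab step 5 | None | Scan 1 |
| Interval to Visit 2 | Length not stated | – | None |
| Seat, ensure fit | Visit 2 | Fit correction, if any | None |
| Occlusal adjustment | Visit 2, same step | Occlusal correction | None |
| Final scan | Visit 2 | None | Scan 2 |

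Fit correction and occlusal correction both fall between scan 1 and scan 2, and no scan separates them. The comparison is described for scans of the device. Section 5.2 limits the objective to the occlusal surface, but the measurement steps define no crop or region that applies this limit. The deviation-scale sentence describes a display of deviations; it does not say which surface enters the RMS. No repeat scan or unadjusted splint is described from which the unrelated change could be estimated.

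**Illustration of size (all values assumed)**

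Let *o* be the RMS due to occlusal adjustment and *e* the RMS due to any other change, both averaged over the same compared surface. If the two are uncorrelated over that surface,

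observed RMS = √(*o*² + *e*²).

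The cross-product is also zero when the two changes lie on different areas of one compared surface, as with a fitting-surface correction in a whole-device comparison. The formula ignores any shift of the best-fit alignment.

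For a true contrast of 0.05 against 0.10 mm and *e* = 0.02 mm:

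- √(0.05² + 0.02²) = √0.0029 = 0.054 mm
- √(0.10² + 0.02²) = √0.0104 = 0.102 mm
- observed difference 0.048 mm against a true 0.050 mm, a loss of about 4%

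The same steps give:

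| True contrast (mm) | *e* (mm) | Observed (mm) | Difference (mm) | Loss |
|---|---|---|---|---|
| 0.05 vs 0.10 | 0.02 | 0.054 vs 0.102 | 0.048 | 4% |
| 0.05 vs 0.10 | 0.05 | 0.071 vs 0.112 | 0.041 | 18% |
| 0.05 vs 0.10 | 0.10 | 0.112 vs 0.141 | 0.030 | 41% |
| 0.10 vs 0.20 | 0.02 | 0.102 vs 0.201 | 0.099 | 1% |
| 0.10 vs 0.20 | 0.05 | 0.112 vs 0.206 | 0.094 | 6% |
| 0.10 vs 0.20 | 0.10 | 0.141 vs 0.224 | 0.082 | 18% |

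The difference in means is shown because the synopsis plans an ANOVA on means. An *e* that is the same in every group does not cancel: it raises every RMS and narrows the gap. The loss is negligible when *e* is small relative to *o*, and considerable when they are of similar size. The documents do not say which case applies.

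**The case against.** The strongest reply is that the plan never says the fitting surface will be altered. Ensuring a proper fit can be read as a check, and the only alteration named is occlusal. This stands to the extent that fit correction is implied and not stated. The right claim is that it can be counted, not that it is. Section 10.3 does list fitting as a separate act, and no rule says what happens if the splint does not seat.

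Second, the synopsis and section 5.2 confine the target to the biting or occlusal surface, and a fitting-surface correction lies on the opposite face. If the RMS were cropped to the occlusal surface, such a correction would not be counted directly; only a shift in alignment or a distortion could carry it over. This is a good argument for writing the crop into the measurement steps, where it is now missing.

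Third, the synopsis also frames the endpoint as less modification at the fit appointment. On that wording a scan of the splint as it leaves the lab is a defensible baseline. It serves less well the aim, also in the synopsis, of judging how accurately the bite was captured.

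A reader might also infer three stronger things, none of which the documents support:

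- **Shape change in storage.** The interval to Visit 2 has no stated limit, but nothing in the documents says the printed splint changes during it.
- **A spray difference between scans.** Spray is named for scan 1 and not repeated for scan 2. The stated reason for it, translucency, applies equally to both, and scanning again is naturally read as repeating the procedure. This is an unspecified condition, not a documented difference.
- **Bias from longer waits in the facebow groups.** All groups share the same design, print, polish and scan steps, and no waiting times are given.

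**Conclusion.** The point holds as a modest weakness in measurement. Followed as written, the plan has no scan between seating and occlusal adjustment and no stated occlusal crop, so any fit correction made at Visit 2 can enter the trial's only outcome under the name of occlusal adjustment. The likely effect is added noise and some dilution of group differences. No bias between groups is shown.

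The size cannot be determined from the documents. Across the assumed values the loss of contrast runs from about 1% to about 41%. The upper end requires unrelated change as large as the larger of the two true values, so it should not be taken as an expected figure. The result rests on some fit correction taking place and on the comparison covering the surface where it is made.

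**What to change.** Amend section 6.1 as follows.

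1. Move scan 1 from lab step 5 to Visit 2: after the splint has been seated and any fit correction is complete, and before the first occlusal correction.
2. Take scan 2 after occlusal adjustment with the same scanner and the same spray procedure, and state this for both scans.
3. Restrict the RMS comparison to the occlusal surface named in section 5.2, with the region defined in advance.

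The number of scans stays at two per splint, and only the timing and scope of measurement change. The cost is one amendment, a short wait for the participant while the splint is scanned, and access to the lab scanner on the clinic day. The documents do not say where that scanner is. If it cannot be reached that day, keep the lab scan, apply the occlusal restriction, and record for each splint whether a fit correction was made.

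The amendment should precede the first fitting, because the seated, unadjusted surface cannot be recovered once occlusal adjustment has begun. It will not remove extra occlusal grinding caused by a splint that still seats imperfectly, or error in the best-fit alignment.

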6.2 Flowchart

8 Participant selection

A recruitment volunteer sheet will be distributed. The recruitment will only occur through the college advert and this project does not have any incentives. When they show interest in this project, I will send them the consent form. Then they will be given 48 hours to decide if they want to take part before being asked to give their consent. Volunteers themselves will need to sign the form. There is no professional Word in this project. So, there is no potential language problem.

8.1 Participant inclusion criteria

- Aged between 18 and 65.
- Able to provide informed consent.
- Have no more than one tooth missing per quadrant.
- Not diagnosed with any TMD disorder.
- Not undergoing any active dental treatment.
- Regular attendee to the dentist and have stable dentition and oral health.

8.2 Participant exclusion criteria

- Patients with removable dentures.
- Patients receiving medication for psychological disorders.
- Patients diagnosed with systemic joint disorders.
- Pregnant or lactating women
- Patients who have received TMD treatment in the last 6 months.

9 Study/Trial procedures.

9.1 Participant recruitment

- Recruitment research sheets to advertise about the project and will be distributed and advertised. Clinical records will be examined by the to assess eligibility prior to the clinic. Eligible participants or those for whom clarification is required will be approached by their contacts to discuss study participation. Interested participant will have the study explained to them and be provided with an information sheet and given the opportunity to ask questions. Those who agree to take part will then have their eligibility confirmed and informed consent taken prior to participation in the trial. Following consent, baseline clinical assessments will be performed, and the volunteers randomised. We will keep a record of the number approached and the number of participants who are eligible and agree to participate in the trial. Reasons for excluding participants and reasons for nonparticipation will be recorded.

- Participant will be gifted with amazon vouchers of 50 pounds.

